### 15.6 Safety analysis

Adverse events and adverse device effects will be collected, analyzed and tabulated as needed. Serious adverse events (SAE) and unanticipated adverse device effects (UADEs) will be tabulated separately and analyzed with respect to their severity.

## 16 PUBLICATION PLAN

This study has been registered at clinicaltrials.gov. The results of this study will be made public within 12 months of the completion of the study.

Reference the Clinical Trial Agreement for detailed publication policy information.

## 18 APPENDICES

### Appendix A: Protocol for preparation of LUM015 for injection

#### 1 Purpose

The purpose of this protocol is to describe the dose preparation for the LUM015 Imaging Agent.

#### 2 Materials

- LUM015 Formulated, stored frozen (-20°C)
- Sterile syringe
- 0.45% Saline without glucose

#### 3 Methods

- 1) After reconstitution, storage of LUM015 is limited to 4 hours at room temperature or 24 hours when stored refrigerated between 2°C and 8°C.
- 2) Obtain the most recent accurate weight of the subject in kg.
  - Note: If weight is measured in lbs, multiply value by 0.45359 to obtain kg.  
Example: 155lbs=(155\*0.45359)kg=70.306kg
- 3) Calculate total dose for subject according to protocol.
  - Example: If dose level is 1.0 mg/kg and weight is 70kg, then dose = 1.0\*70=70 mg.
- 4) Obtain the required number of vials to administer the full dose. Each vial contains 10mg LUM015.
  - Example: If 70mg is the required dose, 70/10=7 vials.
  - Example 2: If the dose level is 1.0 mg/kg and the patient weight is 63 kg, the required number of vial for the dose of 63 mg is 63/10 = 6.3; thus 7 vials would be needed for this patient.
- 5) Allow bottles to acclimate to room temperature for 5 minutes.
- 6) Reconstitute each vial of LUM015 with 1mL of 0.45% saline without glucose.
- 7) Combine the calculated dose from the individual vials in one large syringe.
- 8) Ensure the vial is homogeneous in blue color (see Figure 3 below).
- 9) The IV line must be flushed with 10-20 mL of saline just prior to injection of LUM015 and the injection is immediately followed by a saline flush of 10-20 mL.
- 10) Inject slow bolus into the subject (over three minutes).

LUMICELL CONFIDENTIAL

This document is confidential. Do not disclose or use except as authorized.

11) In case of an allergic reaction to LUM015, sites should not discard any residual drug remaining in the used syringe or unused portion of reconstituted vials. This drug should be stored at -20 degrees C until a Luminicell representative notifies the site of how to proceed with the used syringe.

Figure 1: Vial with protective cap

Figure 2: Empty vial with protective cap removed

Figure 3: Dissolved compound

#### 4 Caution

- **Ensure there are no air bubbles in the syringe prior to injection.**
- **Ensure there are no solid particles visible on the side walls of the syringe barrel prior to injection.**
- **Do not use compound if the date has exceeded the expiration date.**
- **Exposure to direct light for more than 5 minutes should be avoided.**

LUMICELL CONFIDENTIAL

This document is confidential. Do not disclose or use except as authorized.

**Appendix A:** Method for removing, orienting, inking and naming the main specimen and shaved cavity margins.

The methods described below are adapted from Cabioglu, et al. (ASO 14:1458-1471; 2007). This method applies to both palpable and non-palpable breast masses.

Procedure:

1. Surgeon performs surgery attempting to obtain grossly negative margins in the main specimen.
2. Surgeon places orientation stitches at the superior and lateral orientations of the main specimen before it is removed from the patient. **It is extremely important to maintain the orientation of the specimen relative to the lumpectomy cavity to be able to correlate LUM images of the cavity with pathology examination of the main specimen.**
3. Surgeon may elect to remove additional tissue based on palpation of the specimen or lumpectomy cavity walls, x-ray imaging of the main specimen (mainly for non-palpable masses) or visual inspection. If additional tissue is removed, the tissue must be labeled as “additional” and include the orientation from where it was removed (see Appendix C for naming convention of resected tissue). For example, if the surgeon decides to remove additional tissue from the medial orientation, then that tissue should be named as “additional medial excision”.
4. Surgeon inks all surfaces of the main specimen using a differently colored ink for each orientation with the kit procured from a third-party vendor by Luminell. This kit is not part of the LUM Imaging System.
5. If additional tissue is removed, the surgeon should ink as many surfaces as possible maintaining the same color used for a given orientation in the main specimen. For example, if the superior orientation of the main specimen is inked yellow, then the margin side of a SCM from the superior orientation should be inked yellow.
6. All tissue is sectioned in the surgical pathology suite serially in 3-5 mm sections.
7. When therapeutic SCMs are removed, the margin side should be marked with a stitch. These therapeutic SCMs should be named as specified in Appendix C. The opposite side from the stitch must be imaged with the LUM Imaging Device in the operating room. These shaves should be inked per institution’s standard procedure.
8. When selective or comprehensive SCMs are removed, the margin side should be marked with a stitch. These SCMs they should be named as specified in Appendix C. These shaves should be inked per institution’s standard procedure.

LUMICELL CONFIDENTIAL

This document is confidential. Do not disclose or use except as authorized.

## Appendix B: Guidelines for naming of resected tissue

To facilitate data collection and analysis standard naming convention must be used to label all the resected tissue at all sites. Table C1 below provides the guidelines for naming resected tissue. This naming convention must follow the resected tissue since its removal to the final pathology report.

Table C1: Guidelines for naming resected tissue.

Tissue	Naming convention	Example case	Naming example
Main specimen	Main specimen [side of breast]	Main specimen removed from the left breast	Main specimen, left breast
Additional tissue resected based on palpation, visual inspection and/or X-ray imaging of intact main specimen	Additional [orientation]	Additional tissue removed from superior due to palpation of main specimen	Additional superior
Therapeutic shaves	[Orientation] [sequential shave number for an orientation] Therapeutic	First therapeutic shave from medial orientation	Medial 1 Therapeutic
Standard of care shaves	[Orientation] 1 SOC	SOC shave from superior margin	Superior 1 SOC

LUMICELL CONFIDENTIAL

This document is confidential. Do not disclose or use except as authorized.

**Appendix D:** Site-specific sub-study to evaluate complement activation for LUM015 investigational agent

A select number of institutions will participate in a sub-study to evaluate complement activation of LUM015.

**Rationale/Background:**

LUM015 is a fluorescence-based imaging agent that accumulates within and around cells. LUM015 is administered in the main study to the patient via intravenous injection 4 ± 2 hours prior to surgery.

In order to understand the potential of LUM015 to induce a Type I hypersensitivity response in patients, changes in levels of three readily determined clinical lab measures (serum histamine, tryptase and complement) associated with a Type I response are to be evaluated in a cohort of patients that receive LUM015. As any such responses occur promptly after parenthelial exposure to a hypersensitivity inducing moiety, vital signs and blood samples are to be collected prior to LUM015 injection and at 15, 30 and 60 minutes post injection.

**Primary objective:** Evaluate complement activation of LUM015 via analysis of vital signs, tryptase, histamine, and total complement levels in patients being injected with LUM015

**Enrollment:** 10-25 patients will be enrolled at 2-3 selected institutions.

**Schedule of Events: Day 1\***

Histamine	Tryptase	Total Complement	Vital Signs a
Pre-Dose	Pre-Dose	Pre-Dose	Pre-Dose
15 Minutes	15 Minutes	15 Minutes	15 Minutes
30 Minutes	30 Minutes	30 Minutes	30 Minutes
60 Minutes	60 Minutes	60 Minutes	60 Minutes

\*All safety labs and vital signs should be collected prior to subjects going into surgery.

aVital Signs should include Temperature and Blood Pressure

Review the Lab Manual for processing and shipping instructions of the samples to the central lab.

**Statistical Analysis Plan**

All numerical data (histamine, tryptase, total and differentiated complement) will be input into a formatted NCSS data base and then curated using graphical and numeric methods. Once the data sets have thus been verified, each variable will be analyzed for differences from baseline at each

LUMICELL CONFIDENTIAL

This document is confidential. Do not disclose or use except as authorized.

of the time points by ANOVA followed by a suitable *post hoc* analysis. *P* values of 0.05 or less will serve as the criterion for difference being considered significant for endpoints.

Gad SC. (2005) *Statistics and Experimental Design for Toxicologists and Pharmacologists*, 4th Ed. CRC Press, Boca Raton, FL.

LUMICELL CONFIDENTIAL

This document is confidential. Do not disclose or use except as authorized.

**STATISTICAL ANALYSIS PLAN FOR LUMICELL PROTOCOL NUMBER
CL0006r04**

SAP Version Date: 05MAY2021

Study Title: FEASIBILITY STUDY PHASE C: EXPANSION INTO MULTIPLE INSTITUTIONS FOR TRAINING IN THE USE OF THE LUM IMAGING SYSTEM FOR INTRAOPERATIVE DETECTION OF RESIDUAL CANCER IN THE TUMOR BED OF FEMALE SUBJECTS WITH BREAST CANCER

System: LUM Imaging System (LUM015 imaging agent and LUM Imaging Device)

Authors:

[name].
Senior VP, Clinical Research and Strategy
Lumicell, Inc.
[contact]
[contact]

[name].
Principal Data Scientist
Lumicell, Inc.
[contact]

[name].
Professor of Biostatistics
Department of Biostatistics
Boston University
[contact]

LUMICELL CONFIDENTIAL

This document is confidential. Do not disclose or use except as authorized.

TABLE OF CONTENTS

1	Introduction.....	2
2	Analysis Populations	2
3	Efficacy metrics analysis.....	2
3.1	Definition of positive margins	2
3.2	Removal of residual cancer (co-primary endpoint in pivotal study)	2
3.3	Diagnostic performance analysis (co-primary endpoint in pivotal study)	3
3.4	Other analyses (secondary endpoints in pivotal study).....	5
3.5	Safety measurements analysis	6
3.6	Exploratory measurements.....	6
4	Statistical Methods.....	6
4.1	Demographic and baseline characteristics	6
4.2	Residual cancer removal.....	7
4.3	Diagnostic performance (sensitivity, specificity and Youden Index).....	7
4.4	Methods for additional analyses	7
4.5	Safety analysis.....	7
4.6	Protocol Deviations.....	8
4.7	Reported device issues.....	8
4.8	General considerations	8
4.9	Exploratory data	11
5	References.....	11

LUMICELL CONFIDENTIAL

This document is confidential. Do not disclose or use except as authorized.

1 Introduction

This document describes the statistical analysis plan to be performed for the Feasibility Study Phase C in breast cancer patients of the Luminicell Imaging System under protocol number CL0006r04. The objectives of this study are:

- Collect data to refine and verify the tumor detection algorithm
- Complete hands-on training of the surgeons and clinical staff that will be participating in the pivotal study to evaluate the efficacy and safety of the LUM Imaging System in breast cancer surgeries
- Identify and address any site-specific or user-specific issues for using the LUM Imaging System in breast cancer surgeries
- Collect safety and efficacy data

Although no pre-defined, hypothesis tested endpoints were included in the protocol, we will perform data analyses based on the proposed endpoint of the pivotal study protocol CL0007r07.

2 Analysis Populations

- Safety (SAF) population: the safety population includes all subjects who received study drug.
- Modified Intention To Treat (mITT) population: includes all SAF subjects excluding subjects who are not able to be imaged with the LUM Imaging System. That is, the mITT population includes all patients imaged with the LUM Imaging System and will be used as the primary analysis population for the efficacy metrics outlined in section 3.
- Per-Protocol Population: Includes mITT subjects who complete all study evaluations and are without any major protocol deviations. This per protocol population will be used to evaluate the efficacy metrics outlined in section 3.

3 Efficacy metrics analysis

3.1 Definition of positive margins

For this study, positive margins were defined using the latest consensus from the Society of Surgical Oncology as follows:

- For invasive cancer with or without associated carcinoma in situ: cancer cells present on ink [1]
- For pure DCIS lesions: DCIS present within 2 mm from the inked surface [2]. Note: when microinvasive cancer is reported, the positive margin criterion will be the same as for pure DCIS instead of the criterion for invasive cancer per NCCN Clinical Practice Guidelines in Oncology.

3.2 Removal of residual cancer (co-primary endpoint in pivotal study)

The first efficacy metric assesses how much additional residual is identified and removed that would have been missed during the initial standard of care procedure. This metric is defined as the ratio of patients who have **residual cancer** found in at least one LUM-guided shave (also known as therapeutic shave or “T-shave”) among all patients. **Residual cancer** is defined as tumor found

LUMICELL CONFIDENTIAL

This document is confidential. Do not disclose or use except as authorized.

by pathology in a therapeutic shave after the SOC surgical procedure is completed; that is, tumor that current SOC surgery failed to remove (Figure 1). Mathematically, it is defined as:

$$\frac{\# \text{ patients with residual cancer found in at least one therapeutic shave}}{\text{Total number of patients}}$$

[figure not shown]

Figure 1: Depiction of removal of residual cancer analysis.

This proposed primary endpoint for determination of whether tumor is found in at least one therapeutic shave, the **ground truth** of histopathology assessment of the therapeutic shave is used

3.3 Diagnostic performance analysis (co-primary endpoint in pivotal study)

3.3.1 Sensitivity, specificity and Youden Index

[figure not shown]
The second efficacy metrics address the diagnostic accuracy of the system in identifying residual cancer, represented by sensitivity, specificity and Youden Index. The sensitivity, specificity and Youden Index (sensitivity + specificity -1) will be evaluated for the LUM Imaging System after SOC using the hierarchical approach for truth standard as defined below. This analysis also includes the lumpectomy margin sensitivity and specificity for predicting cancer remaining in the cavity as a comparison.

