3.3.2 Definition of truth standard for diagnostic performance

The instrument diagnostic accuracy is measured by sensitivity and specificity on a per-tissue basis. Because a LUM-guided shave does not exist when a negative LUM image is indicated we propose a hierarchical approach to determine the truth standard as depicted in Figure 2. The highest truth standard is whether pathology finds cancer in a tissue shave removed from the area that was imaged in the cavity. When a shave does not exist, then whether tumor is found in a re-excision surgery is considered as the truth standard. When neither a shave nor a second surgery exists for a given orientation that was imaged, the margin assessment of that orientation is used as truth standard. We believe that the hierarchical approach outlined to determine the truth standard is the most meaningful and practical assessment of device accuracy to predict the presence of cancer in the cavity.

LUMICELL CONFIDENTIAL

This document is confidential. Do not disclose or use except as authorized.

True positive = truth standard positive & Lum cavity image positive

False negative = truth standard positive & Lum cavity image negative

True negative = truth standard negative & Lum cavity image negative

False positive = truth standard negative & Lum cavity image positive

Figure 2: Definition of truth standard to evaluate the LUM Imaging System diagnostic performance.

When a therapeutic shave and re-excision are not available for an orientation, the margin from the prior resected tissue of the corresponding orientation will be used as ground inferred truth for evaluation (Figure 3).

The orientation of the tissue removed during a re-excision is typically noted in the pathology report and matches the orientation in which a positive margin was identified from the initial surgery. However, there will be instances in which the orientation of the tissue removed during a re-excision is not specified. In cases of unclear orientation of the tissue removed during re-excisions, it will be assumed that the re-excision was intended to address only the orientations with positive margins and pathology findings from the re-excision (tumor found/not found) will be applied to those orientations.

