4.8.3 Missing and spurious data

During Luminicell-guided imaging, when there is not enough tissue to be removed (e.g. too close to skin or too close to the chest wall) no LUM image shall be recorded because it does not generate an actionable result.

In the case where the LUM Imaging System indicates that a therapeutic shave needs to be removed but the surgeon decides not to follow this guidance, the reason for not doing so will be recorded in the patient's CRF or during imaging. These instances are considered as a protocol deviation. There are other cases when the shavings reach protocol limits so no shaving will be performed. In these cases, the data will be included in the performance evaluation as is - that is no Luminicell-guided shave-taken will be considered as no removing of cancer or positive margin. However, they will be considered as a detection if there are cancer in the re-excision or if there are positive margins on the corresponding orientations.

Occasionally, a cavity image may be recorded from an unintended region or the image may be deemed as low quality (blurry, out of focus, etc.). For example, the surgeon realizes that he/she placed the device in the wrong location within the cavity after recording an image. Since the LUM software does not allow to overwrite saved images, this situation will be documented, the image will be labeled as "image retaken", "eval", "initialscan" or "transient" and the image will be excluded from the analysis. In addition, images labeled as "lens issue" will be considered as a device malfunction and will be excluded from the analysis.

Other cases are handled as follows:

- When a patient was prescribed Letrozole adjuvant therapy prior to surgery, the patient will be removed from the device performance evaluation.
- When the time from injection of LUM015 to lumpectomy incision is greater than 6 hours due to unplanned surgical delays, the patients will be removed from the device performance evaluation.
- For the re-excision rate endpoints, all patients undergoing a re-excision will be included in the analysis.
- When an image is indicated negative by LUM Imaging System but the shave is taken due to X-ray or pathology suggestion, it will be kept for sensitivity and specificity evaluation, however, for the analysis related to margins, it is conditional and described in g.

LUMICELL CONFIDENTIAL

This document is confidential. Do not disclose or use except as authorized.

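### Where no shave or re-excision exists, the lumpectomy-margin comparator appears to be scored against itself, which biases its sensitivity upward and makes its contrast with LUM depend on unstated follow-up rates

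*SAP*

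**What the plan says.** SAP 3.3.1 evaluates LUM sensitivity, specificity and Youden Index after standard of care (SOC), using a hierarchical truth standard. It then adds the comparator: "This analysis also includes the lumpectomy margin sensitivity and specificity for predicting cancer remaining in the cavity as a comparison". No separate truth standard is given for it.

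SAP 3.3.2 defines three tiers:

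- **Shave tier.** "The highest truth standard is whether pathology finds cancer in a tissue shave removed from the area that was imaged in the cavity".
- **Re-excision tier.** "When a shave does not exist, then whether tumor is found in a re-excision surgery is considered as the truth standard".
- **Margin-inferred tier.** With neither of these, "the margin assessment of that orientation is used as truth standard". The section specifies which margin: "the margin from the prior resected tissue of the corresponding orientation will be used as ground inferred truth for evaluation". For an image taken after SOC, that is the SOC margin, which is the comparator.

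The stated reason for the hierarchy is "Because a LUM-guided shave does not exist when a negative LUM image is indicated we propose a hierarchical approach". The last tier is therefore made up mainly of LUM-negative orientations. LUM-positive orientations can also be left without a shave, either by surgeon override or at the shave limit. On the latter, SAP 4.8.3 says "There are other cases when the shavings reach protocol limits so no shaving will be performed". Such orientations stay in the analysis, and "they will be considered as a detection if there are cancer in the re-excision or if there are positive margins on the corresponding orientations".

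**The concern.** In the margin-inferred tier the test and the truth are the same variable. The margin can be neither falsely negative nor falsely positive there, while LUM is marked wrong whenever it disagrees. This is incorporation bias. It acts in two ways:

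- A cancer missed by both tests, with no tissue taken beyond the margin, is recorded as a true negative for both.
- A falsely positive margin that is not re-excised becomes a true positive for the margin and a false negative for LUM.

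The SAP plans no exclusion, by-tier table or caveat for the comparator. SAP 3.3 labels diagnostic performance a co-primary endpoint of the pivotal study, and Protocol 15.5 uses the combined Phase B and C data to estimate the results expected there. An overstated margin sensitivity printed beside LUM could mislead that planning.

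**Working it through.** **Plan's own figure.** The documents give none for the margin comparator. The only sample-size arithmetic, in Protocol 15.2 (32 × 40/19 = 67.4, stated as about 67 patients), reproduces but does not bear on this point.

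**Assumed inputs** (none is in the documents): 1,000 imaged orientations; 5% with residual cancer; LUM sensitivity and specificity 80%/80%; margin specificity 95%; margin sensitivity *s* = 0.30 or 0.50; the two tests independent given disease; every LUM-positive orientation shaved; a fraction *r* of margin-positive, LUM-negative orientations re-excised, with *r* = 1, 0.8 or 0.5.

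**Expected counts**

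- Cancer present: 50, of which 40 are LUM-positive (shaved) and 10 LUM-negative.
- Cancer absent: 950. LUM-positive 190 (9.5 margin-positive, 180.5 margin-negative); LUM-negative 760 (38 margin-positive, 722 margin-negative).

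**Scoring by the SAP hierarchy**

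- Margin true positives = 40*s* + 10*sr* + (10*s* + 38)(1 − *r*) = 50*s* + 38(1 − *r*)
- Margin false negatives = 40(1 − *s*); the true number is 50(1 − *s*)
- LUM true positives = 40; LUM false negatives = 10*s* + 38(1 − *r*)
- Margin true negatives = 902.5 + 10(1 − *s*); margin false positives = 9.5 + 38*r*

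Example, *s* = 0.30 and *r* = 0.8: margin sensitivity 22.6/(22.6 + 28) = 44.7%; LUM sensitivity 40/(40 + 10.6) = 79.1%; margin specificity 909.5/(909.5 + 39.9) = 95.8%.

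| True margin sensitivity | *r* | Margin sensitivity reads | LUM sensitivity reads (true 80%) | LUM/margin ratio (true) | Margin specificity reads (true 95%) |
|---|---|---|---|---|---|
| 30% | 1 | 34.9% | 93.0% | 2.67 (2.67) | 95.0% |
| 30% | 0.8 | 44.7% | 79.1% | 1.77 (2.67) | 95.8% |
| 30% | 0.5 | 54.8% | 64.5% | 1.18 (2.67) | 97.0% |
| 50% | 1 | 55.6% | 88.9% | 1.60 (1.60) | 95.0% |
| 50% | 0.8 | 62.0% | 76.0% | 1.23 (1.60) | 95.8% |
| 50% | 0.5 | 68.8% | 62.5% | 0.91 (1.60) | 97.0% |

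**What drives the contrast.** Both sensitivities share one denominator, so the ranking reverses when 50*s* + 38(1 − *r*) exceeds 40. That means *r* below about 0.61 for *s* = 0.50 (38(1 − *r*) > 15), or below about 0.34 for *s* = 0.30 (38(1 − *r*) > 25). The margin-inferred tier holds 73-75% of orientations, but 727-729 of the 1,000 are negative on both tests. The discordant ones, (10*s* + 38)(1 − *r*), are 0 at *r* = 1, 8.2-8.6 at 0.8 and 20.5-21.5 at 0.5.

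**Incomplete shaving as well.** A second illustration takes LUM 80%/75%, margin specificity 95%, prevalence 3% or 8%, 90% of LUM-positive orientations shaved and 70% of margin-positive, unshaved orientations re-excised. A true margin sensitivity of 40% reads 55-64%, and 70% reads 79-83%. LUM reads 61-78% (true 80%). The sensitivity ratio is 0.99-1.42 (true 2.00) or 0.73-0.94 (true 1.14).

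**Candidate remedies, first set of assumptions**

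- Shave or re-excision pooled: margin specificity = 180.5/(180.5 + 9.5 + 38*r*) = 79.2%, 81.9% or 86.4% for *r* = 1, 0.8, 0.5. LUM specificity = 38*r*/(38*r* + 190) = 16.7%, 13.8% or 9.1%.
- Shave-verified only: margin sensitivity = 40*s*/40 = *s*; margin specificity = 180.5/190 = 95%. Both true values are recovered, given conditional independence.

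**The case against.** **Use of the hierarchy is inferred.** SAP 3.3.1 ties it explicitly to LUM, SAP 3.3.2 speaks of the instrument's accuracy, and SAP Table 1 defines cells for LUM only. Some figures are not shown. This stands as a limit on certainty. Still, placing the margin figures in the same analysis makes the shared hierarchy the natural reading, and if another standard was meant, the SAP does not state it.

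**Follow-up may be nearly complete.** Protocol 3.1 says positive margins dictate a second procedure, and Protocol 8.5 follows such patients through that surgery and its pathology. With full re-excision and full shaving, the ratio is preserved. That is correct, but absolute margin sensitivity is still inflated (34.9% for 30%, 55.6% for 50%). No re-excision rate is given, and SAP 4.8.3 expects some LUM-positive orientations to go unshaved.

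**The stakes are limited.** SAP section 1 says the protocol has no hypothesis-tested endpoints, and no LUM-versus-margin test is planned. Residual cancer removal (SAP 3.2) and conversion to negative margins (SAP 3.4) do not use this hierarchy. The SAP openly calls the last tier inferred truth. All of this stands and limits the consequence to a misleading descriptive comparison.

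A reader might infer that a self-scored share near three-quarters makes the whole comparison invalid. The documents do not support that: under these assumptions nearly all of that share is negative on both tests and enters neither sensitivity, and margin specificity barely moves.

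**Conclusion.** The point holds as a bias in the comparator's absolute sensitivity, and as an unreliable contrast with LUM when follow-up is incomplete. Under the first set of assumptions, margin sensitivity reads 35-55% for a true 30% and 56-69% for a true 50%; specificity reads 95-97% for a true 95%. The upward direction does not rest on those particular values. Within this scoring it needs only cancers that the margin missed in orientations without later tissue, or positive margins left without it. The size does depend on the assumed rates, and the documents supply none of them.

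The tilt toward the margin comes only from discordant margin-inferred orientations, 0.8-2.2% of all orientations in the first illustration when re-excision is 80% or 50%. That is enough to reverse the ranking in one of its six scenarios. The SAP permits such orientations but does not plan to count them. A change to the SAP is warranted; discarding the comparison is not.

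**What to change.** In SAP 3.3.1:

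1. State the truth standard for the margin comparator.
2. Make the lead margin estimate the one in shave-verified orientations, labelled as conditional on those mainly LUM-positive sites. It generalises only if margin and LUM results are independent given disease.
3. Report the margin and LUM 2x2 tables by truth tier, with the number of discordant margin-inferred orientations in each direction.
4. Label any all-tier margin sensitivity as biased upward and not a like-for-like contrast with LUM.
5. Do not pool shave and re-excision for margin specificity. Re-excision is driven by positive margins, and the pooled value falls to about 79-86% against a true 95%. In addition, SAP 3.3.2 assigns re-excision findings of unclear orientation to margin-positive orientations, so the margin also shapes truth in that tier.

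The cost is a few SAP sentences and a filter on data already collected. The price is a smaller, conditional comparison: because the shave-verified set is mainly LUM-positive, LUM's own sensitivity and specificity cannot be estimated on it.
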